7.3 Other Secondary Endpoints

Treatment Cohort

The following efficacy endpoints will be analyzed using baseline values in the previous study (i.e., Study 109, Study 011B, or Study 011B LCI Substudy):

- Absolute change from baseline in LCI_{5.0} (subjects from Study 109 and the Study 011B LCI Substudy only)
- Absolute change from baseline in percent predicted forced expiratory volume in 1 second (ppFEV₁)
- Relative change from baseline in ppFEV₁
- Absolute change from baseline in BMI-for-age z-score
- Absolute change from baseline in weight
- Absolute change from baseline in weight-for-age z-score
- Absolute change from baseline in height
- Absolute change from baseline in height-for-age z-score

- Absolute change from baseline in Treatment Satisfaction Questionnaire for Medication (TSQM) domains
- Time-to-first pulmonary exacerbation, including pulmonary exacerbations in the previous study and the current study (subjects from Study 109 only)
- Event of having at least 1 pulmonary exacerbation, including pulmonary exacerbations in the previous study and the current study (subjects from Study 109 only)
- Number of pulmonary exacerbations, including pulmonary exacerbations in the previous study and the current study (subjects from Study 109 only)

The following efficacy endpoints will be analyzed using baseline values in the current study (Study 110):

- Absolute change from baseline in LCI_{5.0} (subjects from Study 109 and the Study 011B LCI Substudy only)
- Absolute change from baseline in ppFEV₁
- Relative change from baseline in ppFEV₁
- Absolute change from baseline in BMI-for-age z-score
- Absolute change from baseline in weight
- Absolute change from baseline in weight-for-age z-score
- Absolute change from baseline in height
- Absolute change from baseline in height-for-age z-score
- Absolute change from baseline in TSQM domains
- Time-to-first pulmonary exacerbation in the current study (subjects from Study 109 only)
- Event of having at least 1 pulmonary exacerbation in the current study (subjects from Study 109 only)
- Number of pulmonary exacerbations in the current study (subjects from Study 109 only)

The following efficacy endpoints will also be analyzed:

- Rate of change in LCI_{2.5} (subjects from Study 109 and the Study 011B LCI Substudy only)
- Rate of change in LCI_{5.0} (subjects from Study 109 and the Study 011B LCI Substudy only)
- Rate of change in ppFEV₁

Observational Cohort

Not applicable

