In the model, visit will be treated as a class variable, and an unstructured covariance matrix will be assumed to model the within-subject variability. This model imposes no assumptions on the correlational structure and is considered robust. If there is a convergence problem due to the unstructured covariance matrix, the unstructured covariance matrix will be replaced by compound symmetry in the primary analysis. Denominator degrees of freedom for the *F*-test for fixed effects will be estimated using the Kenward-Roger approximation.⁶⁵ With a mixed-effects model as the primary analysis model based on restricted maximum likelihood estimation and assuming that conditional on fixed and random effects, when data are missing at random, no imputation of missing data will be done.

Additional modeling for LCI and ppFEV₁ and similar analyses may be conducted for other continuous variables. Details will be provided in the SAP.

Pulmonary exacerbation-related endpoints will be analyzed based on 109FAS for the active dosing period and separately for the placebo-controlled period for subjects randomized to placebo group in Study 109.

Number of Pulmonary Exacerbations (Subjects From Study 109 Only)

The number of pulmonary exacerbations, both on-treatment events and events after treatment discontinuation, will be analyzed based on 109FAS using a negative binomial regression model. The model will include treatment, weight (<25 kg versus ≥25 kg) and ppFEV₁ severity (<90 versus ≥90), both as determined at screening in Study 109. The data during the placebo-controlled period for subjects randomized to the placebo group in Study 109 will be analyzed using a similar negative binomial regression model without the treatment in the model.

The annualized rate of pulmonary exacerbation, defined as number of pulmonary exacerbations divided by total exposure, will be summarized and plotted using boxplot.

To further examine whether the treatment effect on pulmonary exacerbation was maintained over time, the annualized event-rate, separately for the previous study (Study 109) and the current study (Study 110), will be provided by treatment arm.

Event of Pulmonary Exacerbation (Subjects From Study 109 Only)

The summary statistics including number of subjects (n) and percent will be provided. A bar chart of incidence of pulmonary exacerbations will be provided.

Time-to-First Pulmonary Exacerbation (Subjects From Study 109 Only)

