6.3 Other Secondary Endpoints

Treatment Cohort Period 1

The following efficacy endpoints are defined using baseline values in the previous study (i.e., Study 109 or Study 011B):

- Absolute change from baseline in LCI_{5.0} (subjects from Study 109 and Study 011B LCI Substudy only)
- Absolute change from baseline in ppFEV₁
- Relative change from baseline in ppFEV₁
- Absolute change from baseline in BMI-for-age z-score
- Absolute change from baseline in weight
- Absolute change from baseline in weight-for-age z-score
- Absolute change from baseline in height
- Absolute change from baseline in height-for-age z-score
- Absolute change from baseline in Treatment Satisfaction Questionnaire for Medication (TSQM) domains

The following efficacy endpoints are defined using baseline values in the current study (i.e., Study 110):

- Absolute change from baseline in LCI_{5.0} (subjects from Study 109 and Study 011B LCI Substudy only)
- Absolute change from baseline in ppFEV₁
- Relative change from baseline in ppFEV₁
- Absolute change from baseline in BMI-for-age z-score
- Absolute change from baseline in weight
- Absolute change from baseline in weight-for-age z-score
- Absolute change from baseline in height
- Absolute change from baseline in height-for-age z-score
- Absolute change from baseline in TSQM domains

The following pulmonary exacerbation-related endpoints are defined for subjects from Study 109 only:

- Time-to-first pulmonary exacerbation, including pulmonary exacerbations in the previous study and the current study
- Event of having at least 1 pulmonary exacerbation, including pulmonary exacerbations in the previous study and the current study
- Number of pulmonary exacerbations, including pulmonary exacerbations in the previous study and the current study

The following efficacy endpoints are also defined:

- Rate of change in LCI_{2.5} (subjects from Study 109 and the Study 011B LCI Substudy only)
- Rate of change in LCI_{5.0} (subjects from Study 109 and the Study 011B LCI Substudy only)
- Rate of change in ppFEV₁

Treatment Cohort Period 2 and Observational Cohort

Not applicable

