The analysis of height and height-for-age Z-score will be similar to those specified for the MMRM analysis of LCI_{2.5}, with the absolute change from previous study baseline in height or height-for-age z-score, respectively, at each visit as the dependent variable; and replacing the baseline LCI_{2.5} with baseline height or height-for-age z-score of the previous studies, respectively, as a continuous covariate. Figure for height and height-for-age Z-score will be

plotted similar to absolute change in LCI_{2.5} above. Descriptive summary based on the current study baseline for P-L/I, similar to the summary of LCI_{2.5}, will be provided separately.

Absolute change from baseline in TSQM domains

For TSQM domains, the analysis will be similar to those specified for the MMRM analysis of LCI_{2.5}, with the absolute change from previous study baseline in each domain at each visit as the dependent variable; and replacing the baseline LCI_{2.5} with domain baseline of the previous studies as a continuous covariate. Descriptive summary based on the current study baseline for P-L/I, similar to the summary of LCI_{2.5}, will be provided separately.

Number of pulmonary exacerbations (109 Subjects Only)

The number of pulmonary exacerbations will be analyzed using negative binomial regression model (PROC GENMOD) with two treatment groups: L200/I-L/I based on 109 FAS including events in the Cumulative Study Period, and P-L/I based on 109 ROS including events in the Current Study Period. All pulmonary exacerbation events in each corresponding Study Period will be included.

The model will include treatment (L200/I-L/I and P-L/I), weight (<25 kg and ≥25 kg) and ppFEV₁ severity at screening of the previous study (<90 versus ≥90). The log of time spent for each Study Period (end date of the Study Period – first dose date of the corresponding Study Period +1) in patient-years will be treated as the offset in this model.

The data during the placebo-controlled period for subjects randomized to the placebo group in Study 109 will be analyzed using a similar negative binomial regression model without the treatment in the model. Note the placebo rate might be slightly different from that estimated in Study 109 final CSR analyses, which included two arms (placebo and active) instead of the placebo arm only in this model.

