The annualized (in 48 weeks) event rate of pulmonary exacerbation, defined as number of pulmonary exacerbations divided by total exposure in each study period, will be summarized and plotted using boxplot. In addition, number of events per patient-year with 95% CI from the model will be provided.

Time-to-first pulmonary exacerbation (109 Subjects Only)

Time-to-first pulmonary exacerbation will be analyzed and plotted using the estimates from Kaplan-Meier analysis (KM analysis) in two approaches:

- KM approach 1 includes two treatment groups: 1) L200/I-L/I based on 109 FAS including time-to-first event in the Cumulative Study Period; and 2) P-L/I based on 109 ROS including time-to-first event in the Current Study Period;
- KM approach 2 includes one treatment group, placebo, based on 109 FAS including time-to-first event in the Previous Study Period only.

Both on-treatment events and events after treatment discontinuation will be considered. For subjects enrolled in the Treatment Cohort Period 1 of Study 110, any subject without a pulmonary exacerbation before completion of the eligible analysis period will be considered censored at the end of the analysis period. For subjects not enrolled into the Study 110, any subject without a pulmonary exacerbation before withdrawal from Study 109 will be considered

censored at the time of withdrawal, and any subject who completes Study 109 without a pulmonary exacerbation will be considered censored at the last dose date in Study 109.

Event of having at least 1 pulmonary exacerbation (109 Subjects Only)

Number and percentage of subjects with at least one pulmonary exacerbation will be summarized for treatment groups: 1) L200/I-L/I based on 109 FAS including events in the Cumulative Study Period; and 2) P-L/I based on 109 ROS including events in the Current Study Period.

Number and percentage of subjects with at least one pulmonary exacerbation will also be summarized for Placebo based on 109 FAS including events in the Previous Study Period in a separate column.

Subjects who have no exacerbations through the end of the corresponding Study Period will be considered as having no event. A bar chart summarizing the percentage of subjects with at least one pulmonary exacerbation will be provided.

Rate of change in LCI_{2.5}, LCI_{5.0} (Subjects from LCI Set Only) and ppFEV₁

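### The SAP does not carry over the protocol's by-study exacerbation rates for the L200/I-L/I group, so its pooled rate over about 120 weeks cannot show whether the effect lasted

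*SAP*

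**What the plan says.** Protocol 12.4.3 fits a negative binomial model to exacerbation counts over the active dosing period: "The model will include treatment, weight (<25 kg versus ≥25 kg) and ppFEV₁ severity". A separate model without a treatment term covers the placebo period of Study 109. The protocol then adds a durability display: "the annualized event-rate, separately for the previous study (Study 109) and the current study (Study 110), will be provided by treatment arm". Among the endpoints, Protocol 7.3 includes "Number of pulmonary exacerbations in the current study (subjects from Study 109 only"), with matching entries for time to first exacerbation and for having at least one.

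SAP 10.3.2.2.2 keeps the model and assigns one period to each group: "L200/I-L/I based on 109 FAS including events in the Cumulative Study Period" and "P-L/I based on 109 ROS including events in the Current Study Period". Its terms are the same in kind: "The model will include treatment (L200/I-L/I and P-L/I), weight" and ppFEV1 severity, with log time as offset. Placebo is again fitted alone, over Study 109. The Kaplan-Meier and at-least-one-event analyses use the same assignment of periods. SAP 6.3 keeps only the combined endpoints, for example "Number of pulmonary exacerbations, including pulmonary exacerbations in the previous study and the current study". The sentence promising rates by study and arm is not repeated. What remains is an annualized rate "defined as number of pulmonary exacerbations divided by total exposure in each study period". Durability is still a secondary objective in SAP 5.2.

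**The concern.** A durability question needs an early and a late figure for the same children. In the SAP's exacerbation section, L200/I-L/I gets one modelled rate, one Kaplan-Meier curve and one at-least-one-event percentage, all over the Cumulative Study Period. One average over about 120 weeks cannot separate an early effect that was lost from a small effect that held.

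The placebo figure raises a second problem. It covers only the first 24 weeks, while four fifths of the L200/I-L/I time falls later. A reader who sets the two modelled rates side by side cannot tell drug effect from anything that moved both arms over time, such as age, season or trial participation.

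**Working it through.** **The plan's own figure.** The only precision statement about exacerbations is SAP Table 7-1, at n = 256. The interval p ± 1.96 × √(p(1 − p)/256) at p = 0.1 gives 0.1 ± 0.037 = (0.063, 0.137). The other three rows also match. This table concerns an incidence, and nothing equivalent is given for the count model.

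**Inputs from the documents.** Study 109 lasts 24 weeks and Study 110 lasts 96. One patient-year is 48 weeks (SAP 10.1.2.1). About 200 children come from Study 109.

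**Assumptions.** The documents give no exacerbation rate, dispersion, allocation ratio or rollover rate. I take 100 children per arm, a rate of 0.5 to 1.0 per patient-year, dispersion of 0.5 to 1.0, and full follow-up unless stated.

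**Weights.** Study 109 gives 24/48 = 0.5 patient-years and Study 110 gives 96/48 = 2.0, in total 2.5.

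Pooled rate = (0.5 × r109 + 2.0 × r110)/2.5 = 0.2 × r109 + 0.8 × r110.

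With 80–100% rollover, a mean of 72–96 weeks in Study 110, and 0 or 4 weeks of follow-up, the Study 109 share ranges from 19% to 29%.

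**Waning** (placebo rate constant at 1):

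| Study 109 | Study 110 | Pooled |
|---|---|---|
| 0.60 | 0.60 | 0.60 |
| 0.60 | 0.80 | 0.76 |
| 0.60 | 1.00 | 0.2 × 0.60 + 0.8 × 1.00 = 0.92 |

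Over shares of 19–29%, the last row is 1 − 0.4 × share = 0.92 to 0.88. In reverse, a pooled 0.60 fits (0.2, 0.70), (0.6, 0.60) and (1.0, 0.50) equally well: a worsening, a constant and an improving course.

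**Change common to both arms, no drug effect.** Pooled L200/I-L/I over 24-week placebo is 0.2 + 0.8 × (1 − fall).

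- 10% fall: 0.92
- 20% fall: 0.84
- 30% fall: 0.76 (0.76 to 0.79 over shares of 19–29%)
- 20% rise: 1.16, which would mask a benefit

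The ratio over the same Study 109 weeks stays at 1.00 in every case.

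**How often it would mislead.** I simulated gamma-Poisson counts with no drug effect, omitting the weight and ppFEV1 terms, and compared the pooled L200/I-L/I log rate with the 24-week placebo log rate. Ranges run over the assumed rates and dispersions.

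| Common change | Two-sided Wald test rejects at 5% | 95% CIs do not overlap |
|---|---|---|
| None | 4–5% | about 1% |
| 20% fall | about 10–17% | 2–4% |
| 30% fall | about 18–32% | about 6–12% |

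The two columns answer different questions. Someone comparing printed intervals by eye is closer to the second.

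**The case against.** Several points on the other side are right.

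- **The model is the protocol's.** A reader might infer that the SAP removed a period term. It did not: the protocol's model has none either and also runs L200/I-L/I across both studies.
- **The remaining wording is ambiguous.** SAP 9.1 defines Previous, Current and Cumulative Study Periods, so "defined as number of pulmonary exacerbations divided by total exposure in each study period" could mean all three, which would keep a crude split. It could also mean the one period assigned to each group, which is how the same section uses the phrase for the offset. Even on the generous reading, the modelled rate and its CI stay pooled.
- **The placebo-randomised arm is already split**, as placebo in Study 109 and P-L/I in Study 110.
- **Related information exists elsewhere.** The adverse-event tables (SAP Table 10-4 and 10.4.1) give events per 100 patient-years by preferred term, by study and arm, and Protocol 12.1 names CF lung as the preferred term for exacerbation. Those are coded adverse events rather than protocol-defined exacerbations, and the L200/I columns include Study 011B. The SAP also points to two-arm analyses in the Study 109 report, but these cannot supply the Study 110 rate. The cumulative Kaplan-Meier curve shows timing, for first events only.
- **No test is planned.** SAP 10.3.2.2.1 rules out comparisons between groups, and 10.3.2.3 makes P values nominal. A reader might take the rejection rates above as an inflated type I error of the plan. They are not. They describe an informal reading.

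None of this supplies an early and a late rate of protocol-defined exacerbations, with intervals, for L200/I-L/I.

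**Conclusion.** The point holds as a gap between protocol and SAP. The protocol promised rates by study and by arm, and three current-study exacerbation endpoints. For L200/I-L/I the SAP visibly provides neither, which leaves two of the four study-by-arm cells without a stated estimate. The pooled rate that remains weights Study 110 at about 80% and would report a 0.60 ratio that is wholly lost as 0.92.

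It would go too far to say that waning is hidden everywhere in the outputs, or that the split has certainly been abandoned. The adverse-event tables give a partial view, and the annualized-rate wording might keep a crude version.

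The 0.92 and 0.76 follow from the visit schedule and the assumed rate patterns. The 18–32% and 6–12% also rest on assumed rates, dispersion, arm size and full follow-up. The documents do not say that a 30% common fall is likely. Since durability is a stated secondary objective, this should be corrected before the SAP is final.

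**What to change.** In SAP 10.3.2.2.2:

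1. Restore the protocol's commitment to rates by study and by arm, and define what each study period means in the annualized-rate paragraph.
2. Report annualized rates with 95% CIs for four cells: Study 109 L200/I, Study 109 placebo, Study 110 L200/I-L/I and Study 110 P-L/I.
3. Report the Study 110 to Study 109 rate ratio within L200/I-L/I, with a variance that allows for the same children contributing to both periods.
4. Keep the pooled rate alongside.

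In SAP 6.3, reinstate the three current-study exacerbation endpoints.

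The CIs and the within-group ratio go slightly beyond the protocol's sentence. A model with arm, period and their interaction, fitted by GEE, is one optional way to get all of these estimates; the protocol did not promise it.

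The cost is SAP wording and one more table or model on data already held, with wider intervals per period. On the log scale the standard error of a rate is about √((1/(rate × patient-years) + dispersion)/100). At rate 0.5 and dispersion 0.5, the 95% limits are the estimate multiplied or divided by:

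- Study 109: exp(1.96 × √((1/0.25 + 0.5)/100)) = 1.52
- Study 110: exp(1.96 × √((1/1.0 + 0.5)/100)) = 1.27
- Pooled: exp(1.96 × √((1/1.25 + 0.5)/100)) = 1.25

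The Study 110 cell therefore loses little. Most of the widening falls on the 24-week cells.

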9.1.2 Current Study Period

Current Study Period starts from the first dose date of study drug in Study 110 to the last day in Study 110.

Treatment-Emergent Period for the Current Study Period

The treatment-emergent period for the Current Study Period is the period on or after the first dose of study drug in Study 110 to 28 days (inclusive) after the last dose of study drug in Study 110 or up to the last day in Study 110, whichever occurs first.

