10.2.4 Study Drug Exposure

Treatment Cohort Period 1

Study drug exposure will be summarized for the Previous Study Period based on Safety Set, for the Current Study Period based on 110 Safety Set, and for the Cumulative Study Period based on Safety Set.

Duration of exposure is defined as: last available dose date of the Study Period – first dose date of the same Study Period + 1 day, regardless of 1) unplanned interruptions, 2) the Roll-Over Gap between Previous Study and Study 110 and 3) the 2-week planned wash-out period for subjects from Study 011B for the summary of study drug exposure for the Cumulative Study Period. Duration/cumulative duration of study drug exposure will be summarized descriptively as a quantitative variable (number, mean, SD, SE, median, min, and max) for:

- Previous Study Period (Studies 109/011B) based on Safety Set with two treatment groups (L200/I, Placebo);
- Current Study Period (Study 110) based on 110 Safety Set with two treatment groups (L200/I-L/I, P-L/I) and Overall;
- Cumulative Study Period based on Safety Set with L200/I-L/I, and Current Study Period based on 110 Safety Set with P-L/I, pooled together. The pooled treatment group is presented as L/I Overall.

Additionally, the total duration of study drug exposure, defined as the sum of the subject's duration of treatment exposure and expressed in patient years, will be provided.

Duration/cumulative duration of exposure will also be summarized as a categorical variable: ≥ 1 dose of study drug to <24 weeks, ≥ 24 to <48 weeks, ≥ 48 to <72 weeks, ≥ 72 to <96 weeks, ≥ 96 weeks to 120 weeks, and ≥ 120 weeks.

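### The summary exacerbation rate and the model rate reported beside it appear to use different person-time, so the descriptive rate can run slightly high.

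*SAP*

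**What the plan says.** Three parts of the plan bear on this.

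- **Model (SAP 10.3.2.2.2, number of pulmonary exacerbations).** On events: "All pulmonary exacerbation events in each corresponding Study Period will be included". On person-time: "The log of time spent for each Study Period" is the offset, computed as period end minus first dose plus one day. The period runs past the last dose: "Current Study Period starts from the first dose date of study drug in Study 110 to the last day in Study 110" (SAP 9.1.2). The Cumulative Study Period ends on the same day (SAP 9.1.3).
- **Summary rate and boxplot (same section).** The annualized rate, on a 48-week year, is "defined as number of pulmonary exacerbations divided by total exposure in each study period". The sentence neither defines exposure nor refers to another section.
- **Exposure (SAP 10.2.4).** Duration of exposure is "last available dose date of the Study Period – first dose date of the same Study Period + 1 day", counted through interruptions, the roll-over gap and the 011B washout. Total duration of study drug exposure is "defined as the sum of the subject's duration of treatment exposure and expressed in patient years". The SAP contains no other definition of exposure.

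Protocol 12.4.3 also divides by total exposure for the annualized rate. Its analysis of counts covers "The number of pulmonary exacerbations, both on-treatment events and events after treatment discontinuation".

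**The concern.** A rate is interpretable only if events and person-time cover the same window. Read with SAP 10.2.4, the summary rate stops the clock at the last dose while the events run to the end of the Study Period. The model rate printed alongside it uses the longer clock. The same events would then give two rates, with nothing to tell the reader why they differ.

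A subject-level boxplot is the output most exposed, because a short denominator acts directly on that child's value. The reverse problem is also possible: if exacerbations are not collected after the last dose, the summary rate is sound and the model offset is too long.

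**Working it through.** The documents state no exacerbation rate or event count for this analysis, so there is no planned figure to reproduce. What can be checked is the ratio of the two denominators.

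**Formula.** With the same events in both rates, and E = time from first to last dose in the period:

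summary rate / Study Period rate = (E + time after last dose) / E, which is at least 1.

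The one-day term is ignored; with it, the first result below is 701/673 = 1.042, unchanged to three decimals.

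**Inputs.** Last dose is at Week 96 of Study 110, and the Safety Follow-up Visit is 4 weeks (± 7 days) later (Protocol Table 3-1). Study 109 adds 24 weeks of dosing, giving about 120 weeks cumulatively if there is no roll-over gap.

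**Completers.**

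| Period | 4 weeks after last dose | 3 to 5 weeks after last dose |
|---|---|---|
| Current | 100/96 = 1.042 | 99/96 = 1.031 to 101/96 = 1.052 |
| Cumulative | 124/120 = 1.033 | 123/120 = 1.025 to 125/120 = 1.042 |

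A child with no time after last dose has ratio 1. The Safety Follow-up Visit is not required for those moving straight to commercial drug (Protocol 8.1.1.3) or entering Treatment Cohort Period 2 (SAP Table 13-1).

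**Pooled, with early stopping (assumed).** Let a fraction d stop at week w and a fraction c have no follow-up. Then E = 96(1 − d) + dw and the ratio is [E + 4(1 − c)]/E.

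- d from 0 to 30%, w = 24 or 48, c = 0: excess 4.2% to 5.4%. At the upper end, E = 67.2 + 7.2 = 74.4 and 78.4/74.4 = 1.054.
- Same d and w, c = 50%: excess 2.1% to 2.7%. At the upper end, 76.4/74.4 = 1.027.

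**Individual children with at least one event.**

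- Stop at Week 8 of Study 110 plus 4 weeks: 12/8 = 1.50 in the Current Study Period. Cumulatively, after 24 weeks in Study 109, it is 36/32 = 1.125.
- Stop at Week 24 plus 4 weeks: 28/24 = 1.17 (Current); 52/48 = 1.083 (Cumulative).
- Stop at Week 4 of Study 109, followed to Week 24, not entering Study 110: 24/4 = 6.

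**On the rate scale, for completers, with an assumed true rate of 0.50 per 48 weeks.**

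- Post-dose events captured, Current: 0.50 × 100/48 = 1.042 events over 96/48 = 2 patient-years gives a summary rate of 0.521. Cumulative: 1.292/2.5 = 0.517. The model rate is 0.500 in both.
- Post-dose events not captured, Current: 1.0 event over 100/48 = 2.083 patient-years gives a model rate of 0.480. Cumulative: 1.25/2.583 = 0.484. The summary rate is 0.500 in both.

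**The case against.** The best counter-argument is that the mismatch is inferred. The summary sentence says total exposure without mentioning study drug or citing 10.2.4, and the preceding paragraph uses Study Period time. A programmer could reasonably carry that person-time forward. The instruction to include all period events is likewise given for the model, not repeated for the summary rate. This stands as a limit on certainty. It does not remove the point: the SAP defines exposure only as first-to-last-dose time, and SAP 10.1.2.1 ties the 48-week patient-year to exposure duration.

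It also stands that post-dose capture is unsettled. In the extracted schedules (Protocol Table 3-1, SAP Table 13-1) the row for other outcome events seems to have no mark at the Safety Follow-up Visit. Those tables are broken in extraction, so this cannot be decided here. It does mean that simply copying the model offset into the summary could spread an error.

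Three stronger readings may tempt a reader, and the documents do not support them.

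- **That the summary uses time on drug.** SAP exposure keeps interruptions and gaps; only time after the last dose of the period is lost.
- **That sixfold inflation is typical.** It needs a Study 109 subject who stops at Week 4 and stays to Week 24. Such a child cannot enter the Treatment Cohort (Protocol 9.1), so the case can arise in L200/I-L/I or the placebo period but not in P-L/I, which is drawn from the 109 ROS. A child with no events has rate zero on either denominator.
- **That a treatment comparison is biased.** SAP 10.3.2.2.1 limits efficacy analysis to within-group results, and SAP 10.3.2.3 makes the P values nominal.

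**Conclusion.** The inconsistency in wording is real and its effect is small. Three conditions are needed for inflation: total exposure is read as in SAP 10.2.4, the summary counts the same events as the model, and exacerbations are captured after the last dose. The summary rate then equals or exceeds the Study Period rate, by about 4.2% (Current) or 3.3% (Cumulative) for completers with 4 weeks of follow-up. Individual boxplot values can move more. If post-dose events are not captured, the model rate is the one in error, and it is low. The early-stopping fractions and the 0.50 rate are illustrative assumptions; the documents give neither.

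Severity is minor. The affected output is a descriptive summary of an other secondary endpoint in a study whose primary objective is safety, and the rate with a confidence interval comes from the model.

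**What to change.** In SAP 10.3.2.2.2, use one person-time definition for the offset, the annualized summary rate and the boxplot: Study Period time (end date minus first dose date plus one day), ended at the last date on which outcome events are collected for that subject. Count events over exactly that window in all three. State whether outcome events are collected between the last dose and the Safety Follow-up Visit. Apply the same rule to the placebo-period analysis.

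Because Protocol 12.4.3 also divides by total exposure, record the new denominator as a change from the protocol.

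The cost is a sentence or two in the SAP, one line noting the change, and a small programming edit. No new data are needed.
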